evaluate SAIA-HTN effectiveness on HTN cascade optimization (Aim 1); identify its drivers of implementation success (Aim 2); and determine costs and cost effectiveness on HTN and HIV performance measures (Aim 3). The SAIA-HTN trial was conducted in eight intervention and eight control health clinics, between 2019 and 2023 and over three phases: (1) a 3-month preparatory phase, which included the baseline period from July to September 2020, (2) a 24-month intensive implementation phase in which implementation was supported by the research team, and (3) a 12-month sustainment phase where research team support is removed in Manica and Sofala provinces in central Mozambique. District Health Supervisors, supported by study nurses, will deliver the intervention during the intensive phase, followed by a one-year sustainment phase led by the District Health Supervisors without additional study personnel support. In all 16 health clinics, government health workers provided hypertension care to clients accessing HIV services. Clinician training included a refresher on Mozambique Ministry of Health guidelines on clinical management of hypertension and the use of hypertension treatment job-aids. Both clinicians and data clerks received phone credit vouchers as incentives for the additional work of data collection for the purpose of the study. Sphygmomanometers were allocated to every consultation room where clinicians provided outpatient/HIV services to allow for similar opportunity for hypertension screening in all sites. From July 2020, all 16 sites began to use study data collection tools to collect patient level hypertension care data at every ambulatory care visit, for both new and returning clients. The frequency and schedule of ambulatory consultations was not uniform across clients.

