In eight health clinics assigned to the intervention arm, SAIA-HTN implementation started in October 2020. SAIA is composed of four components – (1) the Hypertension Cascade Analysis Tool – HCAT, (2) Process Mapping, (3) Continuous Quality Improvement – CQI, all of which are operationalized during (4) monthly SAIA meetings. The HCAT uses health facility aggregate patient data to assess the flow of patients through the care cascade, indicate where in the cascade major drop-offs occur, and indicate at which step improvements may result in more patients achieving controlled hypertension. Process mapping consists of a health worker joint assessment of patient paths through hypertension services within the health facility to identify inefficiencies and inconsistencies that may be addressed for improvement. The CQI consists of Plan, Do, Study, Act monthly cycles, in which implementers define a problem based on findings of the hypertension care cascade assessment and process mapping, define and implement solutions to address the defined problem, and iteratively assess the effect of the solutions implemented by reassessing the performance of the hypertension care cascade, reviewing the process map, and sharing anecdotal experiences together. Depending on the perceived feasibility and effectiveness of the solutions implemented during the month, implementers decide if solutions are to be abandoned, adapted for further testing, or adopted as a practice that is to be continued.

The mixed-methods evaluation will evaluate the impact of SAIA-HTN on clinical (controlled HTN, HIV viral load suppressed) as well as process (BP screened, HTN diagnosis, HTN medications prescribed, HTN medications picked up) outcomes. The consolidated framework for implementation research (CFIR) will be used to guide data collection and interpretation related to implementation, to assess fidelity to intervention protocol, describe intervention adaptations when integrated into routine management systems, and identify organizational-level determinants of successful SAIA-HTN implementation. Based on trial results, we will model out the costs and potential benefits on HTN control given different scale-up scenarios within Mozambique. The trial will culminate in a dissemination package, summarizing trial results and providing implementation and cost guidance to support national SAIA-HTN scale-up.

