SAMPLE SIZE AND RANDOMIZATION: Sample size estimation was based on the anticipated absolute difference in the proportion of ambulatory care consults at which hypertension is screened during the last three months of using the SAIA-HTN implementation strategy. Hypertension screening was selected because it is the first step of the hypertension care cascade and its routine use in outpatient visits is recommended by existing guidelines. In the pilot study leading up to this trial, the proportion of ambulatory care consults at which hypertension was screened at the beginning of the pilot was less than 10%, and a 31% increase was observed at the end of the pilot. Assuming an $\alpha = 0.05$ and 1000 HIV care outpatient visits over each 3-month period, we estimated that eight intervention and eight control clusters would be sufficient to have 80% power to detect an absolute difference in the outcome of between 15 and 29%, depending on plausible values of the effect size in the control sites (i.e. 10 to 20% of care consults at which hypertension screening was done) and intra-cluster correlation between 5 and 15%. To select the eight intervention and control clusters, 29 eligible health facilities across the two provinces were stratified by province (Manica or Sofala) and by type (urban or peri-urban) and 1:1 randomized to either intervention or control arm within each stratum, so that two urban and two peri-urban health facilities were allocated for each arm, in each province. Adult (>18 y/o) clients were automatically assigned to either intervention or control arms in dependence of the respective cluster where they access ambulatory care consults.

ANALYSIS APPROACH:

Descriptive analysis

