We described health facility characteristics at baseline and the study participant population both during baseline, and at the time of recruitment for each study phase, in terms of sex, age and hypertension care outcomes status. For the primary process outcome, we describe the number and proportion of outpatient consultations at which blood pressure was screened in each study phase. To describe the hypertension care cascade, we ascertain the proportion of patients who, within the phase they are recruited, are ever screened and diagnosed as eligible for hypertensive treatment, ever receive a prescription and pick-up the medication prescribed, and who present controlled blood pressure control in the last two ambulatory consultations (if same outcome observed in both visits) or in most consultations. Ambulatory consultations beyond the phase of recruitment are censored.

Inferential analysis

To assess the effect of SAIA-HTN, we ascertained clinical outcomes in all ambulatory care visits within each phase (observations attributed to the phase in which consultations took place), and estimated the population level risk of the outcomes using Generalized Estimation Equations (GEE) and Log-binomial or Poisson regressions, assuming an exchangeable correlation structure to account for clustering at the level of health clinic, and adjusted for study phase and for whether patients were newly recruited or retained from a prior study phase (Model 1).

Model 1: $log(E[yij]) = \beta_0 + \beta_1 \cdot x_{ij} + \beta_2 \cdot phase_{ij} + \beta_2 \cdot recruitment_{ij} + u_{ij}$

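### With 16 clinics the GEE plan names no small-sample inference method, so the stated 5% level is not assured; separately, the tested contrast x_ij is undefined.

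*Combined protocol and SAP*

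**What the plan says.** All references are to the combined protocol and SAP.

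- **ANALYSIS APPROACH, Inferential analysis.** The effect is estimated by GEE with log-binomial or Poisson regression, "assuming an exchangeable correlation structure to account for clustering at the level of health clinic". Visits from every phase enter ("observations attributed to the phase in which consultations took place"), and the model is "adjusted for study phase and for whether patients were newly recruited or retained from a prior study phase". The effect term in Model 1 is x_ij, which appears once and is not defined.
- **SAMPLE SIZE AND RANDOMIZATION.** Facilities were stratified by province and by urban or peri-urban type, then "1:1 randomized to either intervention or control arm within each stratum", giving two clinics per arm in each of four strata. At alpha 0.05, "eight intervention and eight control clusters would be sufficient to have 80% power" for an absolute difference of 15 to 29 points, with control screening of 10-20% and ICC of 5-15%.
- **PROCEDURES.** The first phase is "a 3-month preparatory phase, which included the baseline period from July to September 2020". In the intervention clinics, "SAIA-HTN implementation started in October 2020". The three phases last 3, 24 and 12 months.

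The available text ends at the Model 1 equation. It names no robust or model-based standard error, small-sample correction, t or F reference, or permutation or cluster-level test, and it lists no strata terms.

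**The concern.** The sandwich variance of a GEE is justified for a large number of clusters. With 8 clinics per arm it is biased downward, and the normal reference ignores the noise in estimating it. Both make p-values and intervals too small. A plan that says only GEE with exchangeable correlation leaves the analyst free to use the ordinary uncorrected form. A strategy with no effect could then be declared effective about twice as often as the nominal level allows.

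Leaving the randomization strata out acts in the other direction. Stratified allocation balances stratum differences between arms, but a variance computed without strata still counts them as noise. The net error rate therefore depends on how prognostic the strata are, which the documents do not say.

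The undefined x_ij is a second, separate gap. It could be arm over all phases including baseline, exposure after the start in October 2020, or an arm-by-phase interaction. These are different effects, and two analysts following the text could report different ones.

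**Working it through.** **Inputs.** From SAMPLE SIZE AND RANDOMIZATION: 16 clinics, 8 per arm; four strata with 2+2 clinics; alpha 0.05; control rate 10-20%; ICC 0.05-0.15; 1,000 visits per 3 months. My assumptions: a two-sided test, 1,000 visits per clinic (the unit is not stated), and an uncorrected sandwich with a normal reference.

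**Step 1: the plan's own figure.** Effective n per arm = 8m/(1 + (m - 1) x ICC). With m = 1,000 this is 8,000/50.95 = 157 at ICC 0.05 and 8,000/150.85 = 53 at ICC 0.15. The difference detectable with 80% power is 11.5-25.2 points with a pooled z and 12.3-26.5 with t on 14 df. The stated 15-29 is not reproduced exactly, but it is the conservative side. With t on 14 df, power is 91% at 10% v 25% (ICC 0.05) and 87% at 20% v 49% (ICC 0.15). The mismatch reflects unstated formula choices and is not evidence for this point. It does show that a small-sample reference needs no extra clinics.

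**Step 2: hand calculation of the error rate.** Take one period and equal clinic sizes. The GEE arm effect is the log ratio of the two arm means. The uncorrected sandwich variance in each arm is Σ(p_i - p̄)²/(8² p̄²), a divisor of 8 where the unbiased form has 7. The standard error is therefore too small by √(7/8) = 0.935. Rejecting at 1.96 equals rejecting when |t| on 14 df exceeds 1.96 x 0.935 = 1.833, which has probability 8.8%. Clinic proportions near 10-20% are skewed, which can add to this.

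**Step 3: null simulations, strata not prognostic.** Uncorrected sandwich with z, over the plan's rates and ICCs:

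- Single-period arm contrast: 8.6-12.1%, 9.4-12.3% and 9.2-12.1% in three separate sets of runs. A fourth set, which also drew clinic proportions from a logit-normal distribution, gave 8.9-14.5%.
- Three phases, independence working correlation: 8.9-12.2%.
- At a 50% screening rate: about 8-9%.

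**Step 4: effect of the strata.** In the single-period runs the rate was 8.9-14.5%, 6.1-10.8% and 3.5-6.7% when the strata explained 0, 25 and 50% of between-clinic variance (assumed shares). Adding strata terms without a correction gave 13.0-18.8%.

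**Step 5: effect of x_ij.** At a 20% rate, ICC 0.10 and clinic effects constant over phases (2,000 runs each), the rate was 9.5% for arm over all phases, 9.6% for post-start exposure and 9.1% for an interaction. With phase-varying clinic effects and assumed working correlations near 0 and at 0.02, it was 6.8-11.1%.

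**Step 6: the remedies.**

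- Permutation within strata: each stratum has C(4,2) = 6 allocations, so 6⁴ = 1,296 in all, and the smallest two-sided p is 2/1,296 = 0.0015. Simulated size was 4.7-5.8% in one set of runs, 4.3-5.6% in another (single period) and 4.6-5.4% in three-phase data.
- Bias-corrected sandwich with t on 14 df, no strata terms: 4.6-7.8% (Kauermann-Carroll) and 3.6-6.6% (Mancl-DeRouen).

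**The case against.** The strongest reply is that the inflation rests on a default the documents never state. The analysts may have used a corrected variance or a t reference, and text may have followed Model 1 that is not in the available copy. This stands as a limit: the documents do not show that any reported p-value is wrong, only that nothing in the plan prevents it.

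Second, the plan specifies an exchangeable correlation, and the size is less predictable there. With that correlation estimated and clinics drifting between phases, an arm term on follow-up visits gave 7.3-12.4% (strata share 0) and 4.3-7.7% (share 50%) at a drift SD of 0.15 on the logit scale. At a drift SD of 0.30 it gave 1.7-6.5%, among only the 65-77% of fits that converged. A post-start exposure term gave 10.1-15.0%. An all-phase arm term has been checked in too few fits to give a rate under drift, and it may not be inflated. So inflation is not certain. The point is that the size is not controlled.

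Third, several stronger readings are tempting but unsupported.

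- A reader might infer that no error rate is set. Alpha 0.05 is stated, for the sample size.
- A reader might infer that the undefined x_ij causes the inflation. Step 5 shows similar rates under all three definitions.
- A reader might infer that omitting the strata inflates the error. Step 4 shows that it lowers it.
- A reader might quote 15% as the general figure. The single-period peak near that value comes from an analysis the plan does not describe, and the three-phase peak belongs to one possible definition of x_ij.

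**Conclusion.** The point holds in limited form and should be fixed. For 16 clinics the plan leaves the variance estimator, small-sample correction and reference distribution open and ignores the randomization strata. Under an uncorrected sandwich z-test (assumed), the actual size for the screening endpoint is roughly 9-12% when the strata explain little, and it moves toward or below 5% when they explain much. The nominal 5% is therefore not assured in either direction.

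The undefined x_ij is a real but separate defect: it leaves the estimand open and is not the main cause of the inflation.

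The figures assume about 1,000 visits per clinic per quarter and beta or logit-normal clinic proportions. They concern screening only. The second primary endpoint, blood pressure control among treatment-eligible clients, has a different denominator and was not simulated.

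**What to change.** 1. Define x_ij and state which phases it contrasts.
2. Base the test and interval for the primary endpoints on a permutation test within the four strata, using clinic log observed/expected ratios. Subtract the clinic's baseline value if x_ij is post-start exposure. Obtain the interval by inverting the test. State a rule for clinics with zero events, where the log ratio is undefined; this matters most for blood pressure control.
3. Keep a Kauermann-Carroll or Mancl-DeRouen sandwich with a t reference as a secondary analysis. Do not add strata terms without such a correction. In the simulations Model 1 with strata terms failed to converge in 9-46% of runs at drift SD 0.15 and 51-85% at 0.30, so a fallback must be named.
4. Label the change as made after data collection, since the document is dated 10/23/24 and "The SAIA-HTN trial was conducted in eight intervention and eight control health clinics, between 2019 and 2023". Report Model 1 as written alongside.

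**Cost.** No new data or clinics are needed. Relative to the uncorrected z interval, the single-period permutation interval is 26-37% wider if the strata explain nothing, and between 5% narrower and 5% wider if they explain half the between-clinic variance. Simulated power for screening with strata share 0 is 93% at 10% v 25% (ICC 0.05) and 85% at 20% v 49% (ICC 0.15), so the stated 80% is kept at both corners. Kauermann-Carroll with strata terms gives 86% and 78% there, which is a further reason to prefer the permutation test as primary.

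### Model 1 combines an exchangeable clinic correlation with one effect across baseline and later phases; if x is arm, an effective intervention can give a ratio above every true phase ratio, or a failed fit

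*Combined protocol and SAP*

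**What the plan says.** Under ANALYSIS APPROACH, Inferential analysis, the combined protocol and SAP takes outcomes at every visit, assigns each visit to the phase in which it occurred, and fits a GEE with log-binomial or Poisson regression, "assuming an exchangeable correlation structure to account for clustering at the level of health clinic". The model is "adjusted for study phase and for whether patients were newly recruited or retained from a prior study phase". Model 1 has one coefficient for x, additive phase and recruitment terms, and no arm-by-phase term. It does not define x, and no step is given for a fit that fails to converge.

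PROCEDURES describes a 3-month preparatory phase containing the baseline, a 24-month intensive phase and a 12-month sustainment phase. SAIA-HTN began in October 2020, after the July to September 2020 baseline.

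SAMPLE SIZE AND RANDOMIZATION assumes "1000 HIV care outpatient visits over each 3-month period", without saying whether that is per clinic or in total. It states that "eight intervention and eight control clusters would be sufficient to have 80% power" for an "absolute difference in the outcome of between 15 and 29" percentage points, with control rates of "10 to 20% of care consults at which hypertension screening was done" and an "intra-cluster correlation between 5 and 15" per cent.

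**The concern.** Model 1 forces one ratio on all phases. If x is arm, that is wrong by design whenever SAIA-HTN works, because the arms should not differ at baseline. Under independence weighting the misfit is mild: the single ratio is an average of the phase ratios, diluted a little by baseline. Under an exchangeable structure with many visits per clinic, the estimating equation rests on contrasts between phases inside each clinic, and the single ratio need not lie among the phase ratios at all.

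At stake is the main effect estimate. An effective intervention could be reported with an impossible ratio, or the analyst could have to change a non-converging model after seeing the data, with no rule for doing so.

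**Working it through.** **1. Cluster size.** The phases total 3 + 24 + 12 = 39 months, or 13 quarters. If the 1000 visits are per clinic, a clinic contributes 13 × 1000 = 13,000. If they are a total over 16 clinics, it is 1000/16 = 62.5 per quarter and 62.5 × 13 ≈ 812.

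**2. The plan's own figure.** With d the detectable difference, d = (t + z) × √{[1 + (m − 1)ICC] × [p0(1 − p0) + p1(1 − p1)] / (7m)}, where p1 = p0 + d, t = 2.145 (14 df, two-sided 0.05), z = 0.842, m = 62.5, and 7 is 8 − 1 clusters.
- p0 = 0.10, ICC 0.05: the design effect is 1 + 61.5 × 0.05 = 4.075, so d = 15.2 points.
- p0 = 0.20, ICC 0.15: the design effect is 10.225, so d = 29.2 points.

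This matches 15 to 29. No variant tried with 1000 visits per clinic matched both ends. Only two of the many variants matched, so this does not settle the reading, and both sizes are carried forward.

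**3. Mechanism.** With exchangeable correlation a and N visits in a clinic, the Poisson score for the arm term weights each visit's Pearson residual in proportion to √μ − c × (clinic mean of √μ), where c = Na/[1 + (N − 1)a]. Take a = 0.05, visits in the ratio 1:8:4 and, for illustration, fitted rates of 15/20/20%. Then √μ = 0.387, 0.447, 0.447, with mean 0.4426.
- N = 13,000: c = 650/650.95 = 0.9985. The weights are −0.055 at baseline and +0.005 later.
- N = 812.5: c = 40.625/41.575 = 0.977. The weights are −0.045 and +0.015.
- Independence (c = 0): +0.387 and +0.447.

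Suppose the true ratios are 1/2/2 and the phase terms are held at the control rates. For any fitted common ratio between 1 and 2, intervention-arm residuals are negative at baseline and positive later. With the exchangeable weights both products are positive, so the equation cannot balance inside the range and the estimate is pushed above 2.

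**4. Simulation, x = arm.** Assumed: 16 clinics, control 15/20/20%, clinic SD 0.6 on the logit scale, nominal ratios 1/2/2, Poisson. Clinics were either stable or had a between-phase correlation of 0.8.

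| Visits per clinic | Exchangeable: converged | Exchangeable: median ratio | Independence |
|---|---|---|---|
| about 13,000 | 6% (stable) to 33% (0.8) | 61 (stable) to 17 (0.8) | all converged, about 1.8-1.9 |
| about 812 | 94-97% | 2.8-3.0 | all converged, about 1.8-1.9 |

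The independence value is near its expected average: (150 + 2 × 2400)/(150 + 2400) = 4950/2550 = 1.94 at the nominal rates.

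**5. The plan's own effect sizes, x = arm.** Here 10% rises to 25% (ratio 2.5) and 20% to 49% (ratio 2.45), with flat control rates assumed and 200 trials per setting. At 13,000 visits all 200 Poisson fits failed in each of the four settings. At 806 visits (62 × 13):
- 10% to 25%: 22 failed at ICC 0.05 and 87 at ICC 0.15, with converged medians of 4.2 and 13.0.
- 20% to 49%: 128 and 171 failed, with converged medians of 4.2 and 13.3.

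Independence medians were 2.3-2.5 throughout. Log-binomial does not remove the problem: with control 10/20/20%, ratios 1/2.5/2.5, ICC 0.10 and 13,000 visits, the median was 9.7, against 16.7 for Poisson.

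**6. x = post-baseline exposure.** With equal later ratios and stable clinics, the exchangeable fit converged on target. With waning from 2.0 to 1.6, about 44-56% converged at 13,000 visits, and those estimates were in range. At 812 visits no fit was lost.

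**7. Where the exchangeable fit is sound.** With no effect and stable clinics at 13,000 visits, its 5-95% range was 0.73-1.35. With a constant ratio in all phases and stable clinics, it was on target. With arm-by-phase terms (true intensive ratio 2.5), 0 of 150 fits failed and the median intensive ratio was 2.58-2.60, against 2.60-2.63 under independence.

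**The case against.** The best defence is that the working correlation is not the root fault. Once arm-by-phase terms are in the model, exchangeable and independence fits agree and both converge; when x is exposure with a constant effect, exchangeable is the more precise choice. That stands. A reader might infer that exchangeable correlation is unsafe whenever a covariate such as phase varies within a clinic. Step 7 shows otherwise: the damage needs exchangeable weighting and a misfitting mean model together.

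Three other strong inferences also fail.
- That the fit is unreliable even with no effect. Wide null ranges (0.19-3.94 and 0.32-4.09 in two checks) appeared only when clinic rates were assumed to drift between phases, at correlation 0.8. The documents give no drift figure.
- That the harm is the same under either coding of x. Under exposure coding it is a visible failure to converge, not a misleading ratio.
- That 13,000 visits per clinic is the plan's figure. It is one reading. On the other, the bias under arm coding is smaller but still present.

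It is also fair to say that the document is dated after the trial and describes the analysis in the past tense, and that only Model 1 is given. Nothing shows that the reported estimate was in fact wrong or unobtainable.

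**Conclusion.** The concern holds for Model 1 as written when x is arm, a natural reading of an undefined term. An effective intervention then breaks the single-ratio assumption by design. With nominal ratios 1/2/2, the exchangeable estimate lies above every true phase ratio: median 2.8-3.0 at about 812 visits per clinic, and 17 to 61 among the minority of fits that converge at about 13,000. If x is exposure, the risk is limited to non-convergence under waning with large clinics.

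The sizes rest on assumed phase-specific control rates, clinic spread, between-phase correlation and size of waning, none of which the documents give. The direction follows from the weights in step 3. The simulations address visit-level screening; the blood pressure control endpoint, confined to medication-eligible clients, was not simulated.

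**What to change.** In ANALYSIS APPROACH, Inferential analysis:
- Define x as the randomised arm of the clinic.
- Add arm-by-phase terms, so that the SAIA effect is the post-baseline contrast between arms, and say whether it is taken relative to the baseline arm ratio.
- Replace the exchangeable structure with an independence working correlation and a clinic-level robust variance, small-sample corrected for 16 clinics. This still accounts for clustering.
- Keep the exchangeable fit as a sensitivity analysis only, and state what is done if a fit does not converge.

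Both main changes are needed. Independence alone would leave x undefined and, under arm coding, would still average baseline into the effect.

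The cost is a few lines of text and one software option, plus precision. Against a correctly specified exchangeable exposure model, the SD of the log ratio is about 0.19 v 0.05-0.12 at 13,000 visits per clinic, and 0.20 v 0.10-0.14 at 812. The plan should state this loss.

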OUTCOME DEFINITION: The study has two primary endpoints. The first is a process outcome and measures the activation of the hypertension care cascade – the proportion of ambulatory care consults for PLHIV at which blood pressure was screened. The second is a patient level clinical outcome – the proportion of clients eligible for hypertensive medication who attain blood pressure control. Hypertension medication eligibility was guided by a simplified risk stratification tool, but ultimately established by clinicians. This tool describes eligibility as an additive risk score of at least 3 according to the following parameters: 1) score of three for PLHIV previously on or presently initiating hypertensive medication and/or with blood pressure of at least 160/100 mmHg; score of two for blood pressure between 140/90 mmHg and 160/100 mmHg, score 1 for the presence of any number of non-modifiable risk factors (such as previous Myocardial Infarction, Coronary Vascular Disease and Diabetes Mellitus); and score of 0.33 for any number of modifiable risk factor (such as smoking, overweight, and sedentarism). Controlled hypertension is defined as blood pressure reading of ≤140/90 mmHg in clients with verified hypertension. Between these two endpoints, we also assess the proportion of patients that successfully progress from being screened, to treatment eligible, to receiving a prescription, to accessing the prescribed medication and to attaining blood pressure control.

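### Model 1 puts one coefficient on an undefined x_ij across baseline, supported and unsupported months, so the effect it estimates depends on a coding the plan does not state

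*Combined protocol and SAP*

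**What the plan says.** Under ANALYSIS APPROACH, Inferential analysis, the plan states that "we ascertained clinical outcomes in all ambulatory care visits within each phase (observations attributed to the phase in which consultations took place"). It fits log-binomial or Poisson GEE, "assuming an exchangeable correlation structure to account for clustering at the level of health clinic", and the result is "adjusted for study phase and for whether patients were newly recruited or retained from a prior study phase (Model 1"). The printed formula has one term β₁·`x_ij` plus main effects for phase and recruitment. It does not define `x_ij`, shows no arm-by-phase term and has no term for province or facility type. The supplied text stops there.

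Under PROCEDURES there are three phases: 3 months preparatory (containing the July–September 2020 baseline), 24 months with research support and 12 months without it. The intervention clinics started in October 2020. The Descriptive analysis section, by contrast, names baseline separately: "the study participant population both during baseline, and at the time of recruitment for each study phase".

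OUTCOME DEFINITION gives two primary endpoints, neither with a time window: "the proportion of ambulatory care consults for PLHIV at which blood pressure was screened" and "the proportion of clients eligible for hypertensive medication who attain blood pressure control". SAMPLE SIZE AND RANDOMIZATION rests on the "anticipated absolute difference in the proportion of ambulatory care consults at which hypertension is screened during the last three months" of using the strategy, and assumes "1000 HIV care outpatient visits over each 3-month period". Randomisation was stratified by province and by urban or peri-urban type.

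**The concern.** One coefficient can stand for one effect only if the effect is the same wherever `x_ij` is switched on. Three codings fit the text:

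1. `x_ij` = arm, with baseline visits included.
2. `x_ij` = arm after baseline and 0 before it.
3. `x_ij` = arm, with baseline visits left out.

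Under coding 1, visits made before the intervention existed are assigned the same effect as later visits, so the model is wrong even in the simplest case. Under codings 2 and 3 the coefficient mixes supported and unsupported months. A reader would not know which effect is being reported as the effect of SAIA-HTN. Under coding 1 the reported size could be well off in either direction.

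**Working it through.** **The plan's own figure.** The inputs are 8 clinics per arm, α = 0.05 (two-sided assumed), 80% power, control rate 10–20% and ICC 0.05–0.15. I read the 1000 visits as the total over 16 clinics, so m = 1000/16 = 62.5 per clinic. The effective size per arm is n_eff = 8m/(1 + (m−1)·ICC).

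- ICC 0.05: 500/4.075 = 122.7.
- ICC 0.15: 500/10.225 = 48.9.

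With SE = √(2·p̄(1−p̄)/n_eff), where p̄ is the mean of the two rates, and a noncentral t on 16 − 4 = 12 df, the detectable differences are 14.8 points (10% control, ICC 0.05) and 29.4 points (20% control, ICC 0.15). The stated range of 15 to 29 is reproduced. If 1000 is per clinic, a pooled z test gives 11.5 to 25.2 points, so the stated range would be conservative. The first reading implies 1000/(16 × 3) ≈ 21 visits per clinic per month, and the second about 333.

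**Constant effect (assumed 10% to 25% from October 2020, true ratio 2.50), independence.** With equal visits per month and per arm, exp(β₁) is the ratio of arm totals.

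- Coding 1: (3 × 10 + 36 × 25)/(39 × 10) = 930/390 = 2.38.
- Codings 2 and 3: (36 × 25)/(36 × 10) = 2.50.

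**The same effect, exchangeable correlation.** I solved Σ X′A^½R⁻¹A^−½(y − μ) = 0 on expected outcomes, with A = diag(μ) (Poisson variance) and the recruitment term omitted. For arm, the equation over an intervention clinic's visits has the form Σ(y − μ) − c·(Σ√μ)·(Σ(y − μ)/√μ), with c = ρ/(1 + (n−1)ρ). At 21 visits per month, n = 39 × 21 = 819. With ρ = 0.05, n·c = 819 × 0.05/41.9 = 0.98. The second term almost cancels the clinic total, and the misfit between baseline and later months then drives β₁. The solution is 4.30 for coding 1 and 2.50 for codings 2 and 3. With one record per clinic-quarter (n = 13), n·c = 13 × 0.05/1.6 = 0.41, and coding 1 gives about 2.35 to 2.43. The size and the direction of the error therefore depend on visit volume and on the working correlation.

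Simulation agrees. For this case at 21 visits per month (100 datasets), the medians were 4.71 for coding 1 (87 converged), 2.47 for coding 2, 2.55 for coding 3 and 2.51 for arm × period. With no effect every coding converged, with median ratios of 0.99–1.09.

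**Effect that changes over time, independence.** Assume 10% control and a linear rise to 25% over the eight intensive quarters, then held. The intensive mean gain is 15 × 36/64 = 8.44 points.

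- Codings 2 and 3: (8 × 8.4375 + 4 × 15)/12 = 10.63 points, ratio 2.06.
- Coding 1: 127.5/13 = 9.81 points, ratio 1.98.
- Last intensive quarter: 15 points, ratio 2.50.

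A second assumed path has control at 15%, a rise of 25 points over 12 months held to month 24, then 30% in sustainment:

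| Quantity | Ratio |
|---|---|
| True: intensive / sustainment / last three intensive months | 2.28 / 2.00 / 2.67 |
| Independence: coding 1 / 2 / 3 | 2.10 / 2.19 / 2.19 |
| Exchangeable 0.05–0.10, 21 per month: coding 1 | 3.39–5.75 |
| Same: coding 2 | 2.22–2.23 |
| Same: coding 3 | 2.31–2.44 |

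Separate arm terms for baseline, months 1–21, months 22–24 and sustainment return 1.00, 2.23, 2.67 and 2.00 exactly.

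**Scale.** The sample size uses an absolute difference, and β₁ is a log ratio. Fifteen points is a ratio of 25/10 = 2.50 at 10% control and 35/20 = 1.75 at 20%.

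**The case against.** **The text ends at the formula.** The label Model 1 suggests that others follow, and a symbol key or an arm-by-phase model may lie beyond what was supplied. The formula is also loosely printed: β₂ appears twice, and a `u_ij` appears in a GEE. This limits the point to the supplied text and shortens the fix if a later model exists.

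**A planning basis is not an endpoint.** A reader might infer that the trial analyses the wrong endpoint. The documents do not support that. OUTCOME DEFINITION sets no window, using all visits is consistent with it, and a time-averaged effect can be a valid target. The mismatch is with the sample-size basis only.

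**Screening may not be under Model 1.** The inferential paragraph speaks of clinical outcomes, whereas PROCEDURES classes screening as a process outcome. Applying Model 1 to screening is an inference. If it does not apply, the supplied text has no inferential model for that primary endpoint.

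**Equality is possible by chance.** In the first rising path, a sustainment level of about 38% would make the pooled ratio 2.50. A constant effect is therefore the general condition and not a strict one. It may also be insufficient, because Model 1 conditions on recruitment status, which is measured after randomisation.

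**The magnitudes are assumed.** Trajectories, equal volumes and shares of new patients are not in the plan. The analysis is reported in the past tense, so models were apparently fitted. At 333 visits per month coding 1 had no solution beyond a correlation of about 0.02 in the second path. Nobody should infer from this that the trial's model failed: the 21-per-month reading is the one that reproduces the sample size, and convergence counts depend partly on the solver.

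**Conclusion.** The concern holds for the supplied text and should be fixed. How baseline visits enter is undefined. Under the plainest coding (arm, all visits), a constant true ratio of 2.50 becomes 2.38 under independence and about 4.3 at correlation 0.05 and 21 visits per clinic per month. Under the other codings the coefficient is a 36-month average, for example 2.06 against 2.50 in the last intensive quarter. These figures rest on the assumed trajectories and equal visit volumes.

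Two further inferences are not supported. The 15 to 29 point range is not unobtainable, since it is reproduced above. Nor is a raised false-positive rate shown: the no-effect simulations gave medians near 1, and type I error was not studied. The issue is the size and meaning of the effect. Confidence is moderate because the text stops at Model 1.

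**What to change.** - Define `x_ij`, and state whether and how baseline visits enter.
- Fit arm + period + arm × period with baseline as reference, and report intensive and sustainment effects separately for both primary endpoints.
- State which model covers screening.
- Add province × type as fixed effects.
- As a supplement for screening only, state which quarter is meant by the last three months: July–September 2022 if use ends with the intensive phase, July–September 2023 if sustainment counts. Make it its own period, and report the between-arm contrast as an absolute difference and a ratio beside Model 1. Arm × phase alone would return the 24-month average (2.28, not 2.67, in the second path). Alternatively, state that a time-averaged effect is intended and that it is not the quantity used for power.

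If a later model already gives period-specific effects, define `x_ij`, name that model as primary and add the strata if they are absent.

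**Cost.** The change is to the text, with a refit on data already collected. The trial ran to 2023 and the document is dated 10/23/24, so the quarter contrast must be labelled post hoc. It is less precise: with a constant effect at 21 visits per month its simulated interquartile range was 1.91–3.21, against 2.27–2.74 for coding 2 and 2.06–2.96 for coding 3. The strata cost 3 df (14 to 11). If inference uses t quantiles, which the plan does not say, the interval width changes by √(1−f) × 2.201/2.145, where f is the share of between-facility variance that the strata explain. That is 2.6% wider at f = 0, about even at 5%, and 8–14% narrower at 20–30%. The documents do not give f.
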